APPENDIX 1: DERIVED DATA DETAILS

Study End Date: the earliest of study withdrawal date or last contact visit date

Study Duration: defined in days as study end date minus baseline date +1.

Study Day: post-baseline visit or event date minus baseline date +1. For pre-baseline visits or events, study day is defined as pre-baseline visit or event date minus baseline date. Note there is no study equal to 0.

Age at baseline: defined in years as baseline date minus date of birth +1 divided by 365.25.

Duration of disease: defined in days from initial diagnosis date to study enrollment date.

Duration of ABC/MBC disease: defined in days from ABC/MBC diagnosis date to study enrollment date.

Disease-free interval: time from the end of adjuvant/neoadjuvant treatment to the first disease recurrence.

Paloma-3 disease-free interval: defined in days as the time between first diagnosis of breast cancer and onset of metastatic disease or disease recurrence.

Treatment-free interval: defined in days as the time from last dose of prior chemotherapy to first MBC therapy or first study dose whichever occurred earlier.

Line of Therapy (LOT):

Clinical outcome endpoints will be summarized by LOT which is defined based on the number of therapies taken after initial diagnoses of ABC or MBC, but before palbociclib treatment start:

- 1st line: patients had no LOT in the ABC/MBC setting before palbociclib initiation
- 2nd line: patients had one LOT in the ABC/MBC setting before palbociclib initiation
- 2⁺ line: patients had >1 LOT in the ABC/MBC setting before palbociclib initiation

Best Tumor Response: best overall tumor response recorded from palbociclib treatment start until first documentation of progressive disease. Only response assessments recorded on or before the start date of next subsequent line of treatment will be considered.

Clinical Benefit: a best overall tumor response of complete response or partial response at any time, or stable disease for at least 24 weeks post-study treatment initiation. Only response assessments recorded on or before the start date of next subsequent line of treatment will be considered.

Overall Survival (OS): is defined as time (months) from initiation of the palbociclib combination treatment to date of death, due to any cause.

First Hormonal Therapy After Stage III or IV Diagnosis: the first recorded MBC or adjuvant hormonal therapy after initial diagnosis of stage IIIb or IV MBC or ABC.

Palbociclib Hormonal Partner: the concurrent hormonal therapy recorded while on Palbociclib. If the patient took both LETROZOLE and ANASTROZOLE then the first hormone partner (chronologically) is assigned.

Time from Initiation of Treatment to Initiation of Each Subsequent Line of Treatment: defined in days by subtracting the date of treatment initiation from the date of initiation of each subsequent treatment line and adding 1.

Time from Discontinuation of Previous Line to Initiation of the Subsequent Line of Treatment: defined in days by subtracting the initiation date of the previous line from the initiation date of the subsequent line and adding 1.

Time from the Start to End of Each Treatment: defined in months by subtracting the discontinuation date from the initiation date for each treatment line, adding 1, and then dividing by 30.4.

Charlson Comorbidity Index:

Assign a point score to each condition per Table 5 below. Point scores are then summed within patient to generate an overall score of disease burden.

Table 5: List of Comorbidities Collected at Time of Enrolment

Condition	Point Score
Charlson Comorbidity Index conditions:	
Cerebrovascular disease	1
Chronic pulmonary disease	1
Congestive heart failure	1
Connective tissue disease	1
Dementia	1
Diabetes with end organ damage	2
Diabetes without end organ damage	1
Depression	1
Hemiplegia or paraplegia	2
History of myocardial infarction	1
HIV/AIDS ^[a]	6
Hypertension	1
Mild liver disease	1
Moderate to severe liver disease	3
Use of warfarin	1
Moderate to severe renal disease	2
Peptic ulcer disease	1
Peripheral vascular disease	1
Skin ulcers/cellulitis	2
Other specific comorbidities	
Leukemia	N/A
Lymphoma	N/A
Neutropenia	N/A
Anemia	N/A
Other comorbidities not listed above	N/A
No comorbidities	N/A

[a] AIDS = acquired immune deficiency syndrome; HIV = human immunodeficiency virus.

PFIZER CONFIDENTIAL

ECOG Performance Scale:Developed by the Eastern Cooperative Oncology Group, [name], Group Chair.*

Grade	ECOG PERFORMANCE STATUS
0	Fully active, able to carry on all pre-disease performance without restriction
1	Restricted in physically strenuous activity but ambulatory and able to carry out work of a light or sedentary nature, e.g., light house work, office work
2	Ambulatory and capable of all selfcare but unable to carry out any work activities; up and about more than 50% of waking hours
3	Capable of only limited selfcare; confined to bed or chair more than 50% of waking hours
4	Completely disabled; cannot carry on any selfcare; totally confined to bed or chair
5	Dead

EORTC QLQ-30 Scoring:

15 scales and items are calculated per Table 6 below.

Table 6: EORTC QLQ-30 Scoring Instructions

Scale/Item Label	Scale Name	Item Number	Raw Score (RS) ^[a]	Score
Global health status/QoL	QL2	29, 30	$(I_{29} + I_{30}) / 2$	$[(RS - 1) / 6] * 100$
Physical functioning	PF2	1 to 5	$(I_1 + I_2 + I_3 + I_4 + I_5) / 5$	$[1 - (RS - 1) / 3] * 100$
Role functioning	RF2	6, 7	$(I_6 + I_7) / 2$	$[1 - (RS - 1) / 3] * 100$
Emotional functioning	EF	21 to 24	$(I_{21} + I_{22} + I_{23} + I_{24}) / 4$	$[1 - (RS - 1) / 3] * 100$
Cognitive functioning	CF	20, 25	$(I_{20} + I_{25}) / 2$	$[1 - (RS - 1) / 3] * 100$
Social functioning	SF	26, 27	$(I_{26} + I_{27}) / 2$	$[1 - (RS - 1) / 3] * 100$
Fatigue	FA	10, 12, 18	$(I_{10} + I_{12} + I_{18}) / 3$	$[(RS - 1) / 3] * 100$
Nausea and vomiting	NV	14, 15	$(I_{14} + I_{15}) / 2$	$[(RS - 1) / 3] * 100$
Pain	PA	9, 19	$(I_9 + I_{19}) / 2$	$[(RS - 1) / 3] * 100$
Dyspnea	DY	8	I_8	$[(RS - 1) / 3] * 100$
Insomnia	SL	11	I_{11}	$[(RS - 1) / 3] * 100$
Appetite loss	AP	13	I_{13}	$[(RS - 1) / 3] * 100$
Constipation	CO	16	I_6	$[(RS - 1) / 3] * 100$
Diarrhoea	DI	17	I_7	$[(RS - 1) / 3] * 100$
Financial difficulties	FI	28	I_{28}	$[(RS - 1) / 3] * 100$

[a] "I" indicates item response value. Raw score (RS) is the average of all nonmissing item values if at least $\frac{1}{2}$ the item values comprising the scale are nonmissing. For instance, if I_3 and I_5 are missing but the other 3 item values comprising PF2 are nonmissing, RS is calculated as $(I_1 + I_2 + I_4) / 3$.

EORTC QLQ-30 Categories:

- (1) Worsening is defined as a change from baseline of at least a 10-point decrease in score on the functioning domains and global quality of life and at least a 10-point increase in score on the symptom items.
- (2) Improving/Maintaining is defined otherwise.

PFIZER CONFIDENTIAL

G8 Screening Tool²²⁻²⁴

An index (or total) score is calculated by assigning a score to each item per Table 7 below and summing all scores within patient. If any items are missing, the index score is missing. The score ranged from 0 (heavily impaired) to 17 (not at all impaired).

Table 7: G8 Screening Tool Index Score Calculation

	Items	Possible responses (score)
A	Has food intake declined over the past 3 months due to loss of appetite, digestive problems, chewing, or swallowing difficulties?	0 = severe decrease in food intake 1 = moderate decrease in food intake 2 = no decrease in food intake
B	Weight loss during the last 3 months?	0 = weight loss >3 kg 1 = does not know 2 = weight loss between 1 and 3 kg 3 = no weight loss
C	Mobility?	0 = bed or chair bound 1 = able to get out of bed/chair but does not go out 2 = goes out
E	Neuropsychological problems?	0 = severe dementia or depression 1 = mild dementia 2 = no psychological problems
F	BMI? (weight in kg)/(height in m ²)	0 = BMI <19 1 = BMI 19 to <21 2 = BMI 21 to <23 3 = BMI ≥23
H	Takes more than three prescription drugs per day?	0 = yes 1 = no
P	In comparison with other people of the same age, how does the patient consider his/her health status?	0.0 = not as good 0.5 = does not know 1.0 = as good 2.0 = better
Age		0: >85 1: 80–85 2: <80
	Total score	0–17

PFIZER CONFIDENTIAL

Activities of Daily Living (ADL) Total Summary Scores and Categories:

The activity uses a 3-point Likert scale measuring independence in performing the activity (i.e. bathing, dressing, toileting, etc.). “Unable to do without Assistance” is assigned a score of 1, “Partial Assistance Needed” is assigned a score of 2, and “No Assistance Needed” is assigned a score of 3.

The total/summary score ranges between 6 to 18, where a score of 6 indicates a very dependent patient and a score of 18 represents an independent patient.

All 6 items must be available to yield a summary score.

PFIZER CONFIDENTIAL

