Approximately 80% of breast cancers expressed estrogen receptor (ER), progesterone receptor (PR), or both. Endocrine therapy is the mainstream treatment for the HR+ cancers. Currently, first-line treatment in the ER+/HER2-ABC postmenopausal population typically includes endocrine therapies, such as letrozole, anastrozole, exemestane, fulvestrant, and tamoxifen with time to progression and prolongation of progression free survival (PFS) ranging from 5 to 15 months (Cardoso, 2012; Bergh, 2012; Mehta, 2012). These treatment options are supported by clinical practice guidelines published by the European Society for Medical Oncology (ESMO) and the National Comprehensive Cancer Network (NCCN) as preferred first-line options in patients who are antiestrogen naïve or who are more than 2 years from previous antiestrogen therapy and do not have extensive visceral involvement (Cardoso, 2012; NCCN, 2016). Single-agent treatment with an aromatase inhibitor or tamoxifen has shown limited clinical benefit (Baselga et al 2012; Klijn et al 2000). The selective ER degrader fulvestrant has modest activity in this population of patients (Di Leo et al 2010, 2014) and the development of effective therapies that can address resistance to endocrine therapy is of clinical importance.

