Participation in this study is not intended to change the routine treatment patients receive, as determined by their prescribing physicians; all treatment decisions, type, and timing of disease monitoring are at the discretion of the treating physician and patient. Assessments include patient questionnaires and quality of life (EORTC QLQ-C30, G8 Screening Tool,

PFIZER CONFIDENTIAL

Activities of Daily Living [ADL] Questionnaire), site questionnaires, physician metastatic breast cancer (MBC) treatment selection survey, and **CCI** [REDACTED].

Baseline (or Visit 1) is defined as the date of study enrolment when informed consent is obtained and inclusion/exclusion criteria assessed. The Data Entry Schedule is included in Table 1 and the EORTC QLQ-C30 and Geriatric Assessments in Table 2.

Table 1: Data Entry Schedule

Data Collection and Entry ¹	►	Baseline	During Treatment with Palbociclib	Post Treatment with Palbociclib
		SOC Visit 1	SOC Visit 2 through End of Treatment with Palbociclib	Follow-up through End of Study ²
Informed Consent & Inclusion/Exclusion Criteria		x		
Patient Demographics, Study Site Characteristics, Medical History, Baseline Concomitant Medications, Baseline Metastatic Disease Status		x		
Breast Cancer Diagnosis and Recurrence History		x		
Breast Cancer Treatment ³		x ³	x ³	x ³
Physician MBC Treatment Selection Survey ⁴		x ⁴	x ⁴	x ⁴
Performance Status (ECOG)		x	x	
Clinical Assessments ⁵		x ⁵	x ⁵	x ⁵
CCI				
Laboratory: CBC ⁷		x ⁷	x ⁷	
Adverse Events and Serious Adverse Events ⁸		x ⁸	x ⁸	

SOC = Standard of care; ABC = advanced breast cancer; CBC = complete blood count; ECOG = Eastern Cooperative Oncology Group; MBC = metastatic breast cancer; SAE = serious adverse event

1. Data is collected in accordance with normal standard of care visits, enter all data available per Data Entry Schedule into the electronic data capture system.

2. Follow up through End of Study: Enter data at SOC visits where each subsequent (post palbociclib treatment) MBC treatment regimen is prescribed and at end of study.

3. Breast cancer treatment: including surgery, radiation, systemic chemotherapy, hormone therapy, and/or targeted therapy, in both neoadjuvant/adjuvant and metastatic disease settings, prior to, during, and post palbociclib treatment; supportive care is also collected in the metastatic setting while on this study.

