5 ANALYSIS SETS

FULL ANALYSIS SET

The full analysis set (FAS), also referred to as the Safety Analysis Set (SAS), or quality of life analysis set (QoLAS), is defined as all subjects enrolled in the study and received at least one dose of study medication. The FAS will be used in all analyses unless specified otherwise.

PER-PROTOCOL ANALYSIS SET

The per-protocol analysis set (PPAS) is a subset of the FAS and defined as all subjects enrolled in the study who a) received at least one dose of palbociclib, b) did not have any treatment-free interval (see Appendix 1 Data Derivation Details) and c) had no disease-free interval (see Appendix 1).

CCI

SUBGROUPS

Key measures, such as baseline patient characteristics, comorbidities, prior breast cancer treatments, treatment regimens during and after palbociclib treatment, and clinical outcomes will be assessed for the FAS and by specific subgroups defined by palbociclib hormonal partner and up to two additional subgroups. Patients will be classified into one of two or more levels for each subgroup of interest.

Potential subgroups of interest include:

- Age at enrolment (≥ 70 years / < 70 years)
- Ethnicity (Hispanic or Latino / Not Hispanic or Latino)
- Receipt of prior endocrine treatment (yes / no)
- Eastern Cooperative Oncology Group (ECOG) performance status (0-1 / 2-4)
- Insurance type (public / private / uninsured)
- ABC/MBC diagnosis at enrolment (de novo / recurrent disease)
- Disease stage at initial diagnosis (stage 0-IIIA / stage IIIB-IV)
- Charlson Comorbidity Index (CCI) (0 / 1-2 / 3+)

PFIZER CONFIDENTIAL

- Type of regimens (endocrine only / chemotherapy only / endocrine therapy combined with target therapy)
- Disease-free interval (0-<12 months / 12-<24 months / 24-<36 months / 36+ months)
- Visceral disease at enrolment (yes / no)
- Menopause status (yes / no)
- Line of therapy (LOT) in the ABC/MBC setting (1st line, ≥2nd line]

PFIZER CONFIDENTIAL

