8 STATISTICAL ANALYSIS

This study has a convenience sample; thus, results may not be generalizable to the entire population with the disease. Due to the study's exploratory nature, study measures will be summarized descriptively. Furthermore, any p value reporting should be placed in a descriptive framework for hypothesis generation and any such inferential analysis is intended to guide further research.

All analyses will be conducted using SAS® version 9.4 or higher.

The intention is to analyze all available data. In the advent that COVID may cause gaps in subject data or require adjustments to statistical methodologies, our intent is to address such issues if or as needed. Both ICON and Pfizer have internal guidances and recommendations on file to assist with decision-making with regards to COVID-related data issues and these will be consulted if or as needed.

GENERAL METHODS

For continuous variables, means, standard deviations (SD), medians, minimums, maximums, and missing will be reported. For discrete variables, frequencies and percentages will be reported. Missing or unknown categories for each variable also will be presented. Percentages will be calculated excluding missing or unknown values. 95% Confidence Intervals (CI) are two-sided.

All summaries will be performed for all patients in the corresponding analysis set and by treatment combination defined at study entry within the corresponding analysis set:

- Palbociclib + Letrozole or Anastrozole
- Palbociclib + Fulvestrant
- Palbociclib + Exemestane
- Other

The baseline record is defined as the last observed measurement prior to palbociclib administration. Change from baseline is defined as the post-baseline value minus the baseline value.

Time in days between two dates will be calculated using the formula most recent date minus earlier date plus 1. For time in months, the same formula for days will be applied but then divided by 30.4. For time in years, the same formula for days will be applied but then divided by 365.25.

Variable definitions are found in Appendix 1 Data Derivation Details.

DISPOSITION OF SUBJECTS

A subject disposition summary will be reported. Subjects' study completion date and reason for premature termination will be reported in listing format. Number of subjects with initial diagnosis and with recurrent diagnosis will be reported in table and listing format.

DEMOGRAPHIC AND BASELINE CLINICAL CHARACTERISTICS

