Demographic and baseline characteristics variables will be summarized for the FAS. For continuous variables (i.e., age at study enrollment, weight, height, BMI), summary statistics will be generated. For categorical variables (sex, race, ethnicity, insurance provider), the frequency and percentage of subjects in each category will be presented.

The following disease-related baseline characteristics will be summarized:

- Paloma-3 disease-free interval
- Disease free interval following treatment for early stage disease
- Treatment-free interval
- ABC/MBC diagnosis
- Duration of ABC/MBC disease
- Age of diagnosis
- Disease type
- Disease stage
- Disposition of diagnosis
- Performed biopsy and associated mutations
- Diagnostic imaging performed and imaging method
- Sites of metastases
- Estrogen Receptor (ER)/Progesterone receptor (PR) status
- Human epidermal growth factor receptor 2 (HER2) status
- Visceral status
- ECOG performance status
- Line of therapy in the ABC/MBC setting (1st line, 2nd line, 2+ line)
- Menopause status

MEDICAL HISTORY AND CONCURRENT MEDICAL CONDITIONS

Medical history and concurrent medical conditions will be summarized and presented in tabular and listing format for the FAS.

In addition, the CCI score^{17, 18} will be calculated. See Appendix 1 Data Derivation Details. Note cancer will not be included in the CCI calculation because it is the diagnosis of interest. CCI score at time of enrolment will be summarized and reported in tabular format.

MEDICATION HISTORY AND CONCOMITANT MEDICATION

Summarized information on medication history for the FAS will include:

- Prior therapy for initial diagnosis and the best response
- Prior therapy at ABC/MBC setting and the best response
 - Number of Lines of therapy
 - Therapy categories
 - Best response
- Prior chemotherapy
- Treatment free interval
- Prior radiation therapy
- Months from last prior radiation to first study dose
- Prior surgery or non-radiation procedures

All concomitant medications will be coded by therapeutic classification, subclassification, and medication using the World Health Organization Drug Dictionary (WHO Drug). A concomitant medication is defined as a medication that is ongoing as of Study Day 1, ends on or after Study Day 1, or starts on or after Study Day 1 and no more than 28 days after the last dose of study drug.

Concomitant medication of interest will be reported separately.

STUDY DRUG EXPOSURE

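### The treatment-free interval starts at the last chemotherapy dose only, so adjuvant endocrine therapy counts as treatment-free, and MBC chemotherapy and chemotherapy-naive patients have no workable rule

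*SAP*

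**What the plan says.** SAP Appendix 1 defines the treatment-free interval, in days, as the "time from last dose of prior chemotherapy to first MBC therapy or first study dose whichever occurred earlier". Only chemotherapy starts the clock; any MBC therapy, endocrine included, stops it.

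Chemotherapy and hormone therapy are different things in this plan. The Table 1 footnote on treatment data reads "Breast cancer treatment: including surgery, radiation, systemic chemotherapy, hormone therapy, and/or targeted therapy, in both neoadjuvant/adjuvant and metastatic disease settings". Both documents restrict the cohort to HR+ disease, and Protocol Section 6.1 states "Endocrine therapy is the mainstream treatment for the HR+ cancers". SAP Section 5 also lists prior endocrine treatment as a possible subgroup.

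Patients treated for MBC before palbociclib are included. Appendix 1 has the category "2nd line: patients had one LOT in the ABC/MBC setting before palbociclib initiation", and a further category for more than one earlier line.

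The interval appears twice in SAP Section 8. It is listed among the disease-related baseline characteristics, beside the two disease-free intervals, and again under medication history, directly after the bullet "Prior chemotherapy". Neither place limits that chemotherapy to a setting. The general calculation rule in the same section is "Time in days between two dates will be calculated using the formula most recent date minus earlier date plus 1".

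SAP Section 5 also uses the interval to define the per-protocol analysis set (PPAS): members must be patients who "did not have any treatment-free interval", with a pointer to Appendix 1.

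**The concern.** The label promises time off treatment. The definition delivers time since chemotherapy. For a patient who had adjuvant chemotherapy followed by endocrine therapy, the whole endocrine course falls inside the interval. A patient who relapsed on or just after endocrine therapy can then appear in the baseline table as long untreated.

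Two further gaps follow from the same sentence. A patient treated with endocrine therapy alone has no start date, and the SAP has no rule for that case. And because prior chemotherapy is not tied to the (neo)adjuvant setting, a patient given chemotherapy for MBC may have a start date that falls on or after the end date.

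This is a descriptive study, so its baseline and treatment-history tables are main products. A reader of those tables would take the variable at its name.

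**Working it through.** The SAP gives no figure for this variable, so there is nothing to reproduce. The check applies the definition to illustrative dates. All durations below are assumptions, because the documents state none.

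**Rules used**
- Start: last dose of prior chemotherapy. End: the earlier of first MBC therapy and first study dose (SAP Appendix 1).
- Days = later date − earlier date + 1 (SAP Section 8, General Methods).

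**1. Adjuvant chemotherapy, then endocrine therapy**

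Assume endocrine therapy starts 30 days after the last chemotherapy dose and first MBC therapy starts 30 days after endocrine therapy stops. A year is 365.25 days, and the course length is cut to whole days.

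Reported interval = 30 + endocrine days + 30 + 1. Interval from endocrine stop to first MBC therapy = 30 + 1 = 31.

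| Endocrine course | Endocrine days | Reported interval (days) | Endocrine stop to first MBC therapy (days) | Share of reported interval on endocrine therapy |
|---|---|---|---|---|
| 2 years | 730 | 30 + 730 + 30 + 1 = 791 | 31 | 730/791 = 92% |
| 5 years | 1826 | 30 + 1826 + 30 + 1 = 1887 | 31 | 1826/1887 = 97% |
| 10 years | 3652 | 30 + 3652 + 30 + 1 = 3713 | 31 | 3652/3713 = 98% |

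The overstatement is roughly the length of the endocrine course, whatever that is.

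**2. Endocrine therapy without chemotherapy**

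There is no last chemotherapy dose, so there is no start date and no value. The SAP does not say whether such a patient is missing or not applicable.

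**3. Chemotherapy given for MBC before palbociclib**

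This applies only if prior chemotherapy includes the MBC setting, and only to patients with at least one earlier MBC line. The end is the start of first MBC therapy. The last chemotherapy dose is on or after that date.

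| Assumed MBC history | Signed (end − start) | SAP Section 8 formula |
|---|---|---|
| First-line chemotherapy, 90 days | −90 | 90 + 1 = 91 |
| First-line chemotherapy, 180 days | −180 | 180 + 1 = 181 |
| First-line chemotherapy, 365 days | −365 | 365 + 1 = 366 |
| Endocrine 365 days, 30-day gap, chemotherapy 180 days | −(365 + 30 + 180) = −575 | 575 + 1 = 576 |

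The SAP formula always subtracts the earlier date from the later one, so it returns a plausible positive number. That number is time since first MBC therapy began, which is mostly or wholly time on treatment. A negative value would be caught by a range check; these would not.

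**4. PPAS criterion**

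Under the SAP formula the smallest possible interval is 0 + 1 = 1 day. Every patient with prior chemotherapy and known dates therefore has an interval. Read literally, the PPAS drops all of them. Patients without chemotherapy, however long they were off endocrine therapy, meet this criterion.

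**The case against.** **It may have been meant as a chemotherapy-free interval.** The medication-history list puts it straight after prior chemotherapy, which supports that reading. If so, the first defect is a misleading label and no more. But the baseline list places it beside the disease-free intervals under a name that says treatment, and the PPAS uses it under the same name. The text needs one correction or the other.

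**Much of the information is reported elsewhere.** This stands in large part. Appendix 1 defines a disease-free interval that starts at the end of (neo)adjuvant treatment of any type, and prior therapy for the initial diagnosis is summarised separately. If recurrence falls between stopping endocrine therapy and first MBC therapy in the examples above, that interval is at most 31 days. A careful reader could see the discrepancy.

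**No value for chemotherapy-naive patients is natural for an interval that starts at chemotherapy.** That is fair. SAP Section 8 also requires missing counts to be shown. What is lacking is a rule that separates not applicable from missing.

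**Ending at first MBC therapy suggests that chemotherapy before the metastatic setting was meant.** This is plausible, and the reversed dates are therefore a conditional problem. The text neither states nor excludes it.

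**A reader might infer that the SAP will produce negative intervals.** Under its own general formula it cannot; negative values arise only if a programmer uses signed subtraction. **A reader might also infer that the variable is meant to measure endocrine sensitivity.** The documents give it no such purpose.

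**Conclusion.** The point holds as a definition error of minor consequence. Followed as written, the SAP reports time on adjuvant endocrine therapy as treatment-free for every patient who had chemotherapy followed by endocrine therapy. The illustrative results are 791 to 3713 days, against 31 days between stopping endocrine therapy and first MBC therapy. They rest on assumed courses of 2 to 10 years and 30-day gaps. The documents give neither adjuvant durations nor the share of patients affected, so the effect on a table median cannot be stated.

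The spurious positive interval after MBC chemotherapy (181 days for 180 days of first-line treatment) rests on the further assumption that prior chemotherapy covers the MBC setting.

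It would be tempting to conclude that study results are distorted. The documents do not support that. The variable is not an endpoint, a listed subgroup or a named Cox covariate. The FAS is the default set, and no readable analysis is assigned to the PPAS (part of SAP Section 5 is blacked out). rwPFS, OS and the FAS analyses are unaffected. What is affected is the descriptive baseline and treatment-history tables and the definition of the PPAS.

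**What to change.** Choose one of two definitions in SAP Appendix 1.

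- **(a) Keep the name and widen the start.** Measure from the last dose of any (neo)adjuvant systemic therapy (chemotherapy, endocrine or targeted) to the earlier of first MBC therapy and first study dose. Mark it not applicable for de novo disease and for patients with no (neo)adjuvant systemic therapy.
- **(b) Keep the start and change the name.** Call it the chemotherapy-free interval, limit the start to (neo)adjuvant chemotherapy, and mark it not applicable for patients without such chemotherapy.

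Under either option, count not applicable separately from missing, and state that a start date after the end date is queried and not passed through the general formula.

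Then reconcile the PPAS criterion in SAP Section 5 with the chosen definition. Changing the start date does not solve this by itself. Under (a), a literal reading would drop everyone with prior (neo)adjuvant systemic therapy; under (b), everyone with prior (neo)adjuvant chemotherapy. The SAP should state what the criterion is meant to exclude.

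The cost is one definition, one not-applicable rule and one sentence on the PPAS. Treatment data are already collected in both the (neo)adjuvant and metastatic settings, so no new data are needed.
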